**Table 6 - Analysis windows definition for efficacy**

Time point	Targeted study day	Efficacy analysis window (in study days)
Week 12	85	2 to 126
Week 24	169	127 to 210
Week 36	253	211 to 308
Week 52	365	309 to 406
Week 64	449	>406

Note: Safety and BM will follow the same analysis windows.

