Archive blood samples (protein and mRNA biomarkers) ^v		X								X							X			
Blood DNA for genomics ^w		X																		

- a Randomization/baseline Visit is defined as Day 1. Visit windows for subsequent visits are +/- 2 days.
- b All assessments at Visit 2 (Day 1) are to be conducted predose with the exception of the assessment of local tolerability of SC injections.
- c Supplementary calls may be made to supply IMPs kits directly to patient's home.
- d Study treatment to be administered once a week, either at the site level or at home by a nurse.
- e Complete physical examinations will include skin, nasal cavities, eyes, ears, respiratory, cardiovascular, gastrointestinal, neurological, lymphatic and musculoskeletal systems. [REDACTED] Nail beds (periungual areas) should be examined for "splinter lesions" and digital tuft for tuft purpura or ischemia. Gynecological and urogenital examinations will not be done in this study unless for cause.
- f Vital signs, including blood pressure (mmHg), heart rate (beats per minute) and body weight (kg) will be measured at screening, baseline and every subsequent visit. Height (cm) will be measured at screening (Visit 1) only. BMI will be calculated automatically at all visits.

- g* Hematology: Hemoglobin, hematocrit, red blood cell count, erythrocyte sedimentation rate (ESR), white blood cell count with differential and platelet count. Biochemistry: Fasting glucose, blood urea nitrogen, creatinine, sodium, potassium, chloride, bicarbonate, calcium, phosphorous, total protein, albumin, total bilirubin, alkaline phosphatase, ALT, AST, CPK, hs CRP. Urinalysis (dipstick) to include: specific gravity, pH, glucose, ketones, blood, protein, nitrate, leukocyte esterase, urobilinogen and bilirubin. If any parameter on the dipstick is abnormal, a urine sample should be sent to the central laboratory for testing. If positive for proteins, microscopic analysis is performed by central laboratory.
- h* Serology testing includes hepatitis B surface antigen, hepatitis B surface antibody, hepatitis B core antibody, and hepatitis C antibodies.
- i* [REDACTED]
- j* Tuberculosis screen: history and QuantiFERON-TB Gold test. If result of QuantiFERON-TB Gold test is indeterminate, the test should be repeated.

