 - *Ask patients to come back to the site 1 week later to receive fourth IMP administration and be monitored for at least 1 hour after dosing]*
- Schedule an appointment for Visit 4

10.1.4 Visit 4: on treatment / Week 4

- Record all concomitant medication use
- Inquire about AEs/SAEs
- Review patient booklet to assess local tolerability at the injection site and treatment compliance *[For Czech Republic only, per local requirement: sentence deleted]*
- Record vital signs including blood pressure, heart rate and weight
- Perform a complete physical examination
- Obtain (fasting) blood samples for complete clinical laboratory determinations including hematology and biochemistry profile,
- Obtain urine for urinalysis (dipstick)

- For women of childbearing potential:
 - perform urine pregnancy test. The patients should be instructed to do the urine pregnancy test at home on a monthly basis during the intervals in between on-treatment study visits for the duration of the study. In case of a positive pregnancy test, the patient should be advised to contact immediately the Investigator
 - dispense urine pregnancy test kit for monthly urine pregnancy test (1 month supply)
- Perform 12-lead ECG
- Perform blood sample for serum SAR156597 and for anti-SAR156597 antibodies (ADA)
- Perform blood sample for ANCA
- Perform blood sample for complement (C3, C4 and CH50)
- Call IVRS to register visit and obtain next treatments number
- Dispense and administer IMP
 - [For Czech Republic only, per local requirement:*
 - *Dispense and administer IMP*
 - *Patients will be monitored for at least 1 hour after dosing*
 - *Ask patients to come back to the site 1 week later to receive sixth IMP administration and be monitored for at least 1 hour after dosing]*
- Schedule an appointment for Visit 5

10.1.5 Visit 5: on treatment / Week 6

- Record all concomitant medication use
- Inquire about AEs/SAEs
- Review patient booklet to assess local tolerability at the injection site and treatment compliance *[For Czech Republic only, per local requirement: sentence deleted]*
- Record vital signs including blood pressure, heart rate and weight
- Perform a complete physical examination
- Call IVRS to register visit and obtain next treatments number
- Dispense and administer IMP
 - [For Czech Republic only, per local requirement:*
 - *Dispense and administer IMP*
 - *Patients will be monitored for at least 1 hour after dosing*

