11.4.3 Analyses of safety data

The summary of safety results will be presented by treatment group on the basis of the safety population.

All safety analyses will be performed on the safety population using the following common rules:

- The baseline value is defined generally as the last available value before randomization.
- For quantitative safety parameters based on central laboratory/reading measurements, descriptive statistics will be used to summarize results and change from baseline values by visit and treatment group.
- The analysis of the safety variables will be essentially descriptive and no hypothesis testing is planned.

The following definitions will be applied to laboratory parameters, vital signs and ECG:

- The potentially clinically significant abnormality (PCSA) values are defined as abnormal values considered medically important by the Sponsor according to predefined criteria/thresholds based on literature review and defined by the Sponsor for clinical laboratory tests, vital signs, and ECG.

- PCSA criteria will determine which patients had at least 1 PCSA during the TEAE period, taking into account all evaluations performed during the TEAE period, including unscheduled or repeated evaluations. The number of all such patients will be the numerator for the on-treatment PCSA percentage.

The TEAE observation period is defined as the time from first dose of IMP up to 12 weeks after the last dose of IMP.

Analysis of the adverse event data

Treatment-emergent AEs, treatment-emergent SAEs, TEAEs leading to treatment discontinuation and treatment-emergent AESIs will be summarized for each treatment group based on MedDRA coding of verbatim terms reported by investigators.

Analysis of TEAE

Treatment emergent adverse event incidence tables will be presented by system organ class (SOC) (sorted by internationally agreed order), high-level group term (HLGT), high level term (HLT) and preferred term (PT), sorted in alphabetical order for each treatment group, the number (n) and percentage (%) of patients experiencing at least one TEAE. Multiple occurrences of the same event in the same patient will be counted only once in the tables within a treatment phase. The denominator for computation of percentages is the safety population within each treatment group.

Analysis of all treatment-emergent SAEs

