All treatment-emergent SAEs will be presented by primary SOC, HLGT, HLT, and PT, showing number (%) of patients with at least 1 serious TEAE, sorted by SOC internationally agreed order. The other levels (HLGT, HLT, PT) will be presented in alphabetical order. Listings will be provided for all SAEs by treatment group and patient with flags indicating on-treatment status.

Analysis of all TEAEs leading to permanent treatment discontinuation

TEAEs leading to treatment discontinuation will be presented by primary SOC, HLGT, HLT, and PT, showing number (%) of patients with at least 1 TEAE leading to permanent treatment discontinuation, sorted by SOC internationally agreed order. The other levels (HLGT, HLT, PT) will be presented in alphabetical order. Listings will be provided for all TEAE leading to permanent treatment discontinuation by treatment group and patient.

Analysis of treatment-emergent AESI

Treatment-emergent AESI, by AESI category and PT, will show number (%) of patients overall, sorted by decreasing incidence of PT within each AESI category. The AESIs include, but are not limited to, the following categories and details of the MedDRA coding will be provided in the statistical analysis plan: tuberculosis, anaphylaxis, hypersensitivity, vasculitis.

Analysis of Deaths

The following deaths summaries will be generated:

- Number (%) of patients who died by study period (TEAE, on-study) and reasons for death summarized on the safety population by treatment received
- Death in nonrandomized patients or randomized and not treated patients
- TEAE leading to death (death as an outcome on the AE e-CRF page as reported by the Investigator) by primary SOC, HLG, HLT and PT showing number (%) of patients sorted by internationally agreed order of SOC and alphabetic order of HLG, HLT, and PT.

Analysis of the laboratory data

The summary statistics (including number, mean, median, standard deviation, minimum and maximum) of all laboratory variables will be calculated for each visit or study assessment (baseline, each post-baseline time point, endpoint) by treatment group. Listings will be provided with flags indicating the out of range values as well as the PCSA values.

The incidence of PCSA at any time will be summarized by treatment group for each laboratory parameter. Shift tables showing changes with respect to the baseline status will be provided.

Analysis of the vital signs data

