The summary statistics (including number, mean, median, standard deviation, minimum and maximum) of all vital signs variables will be calculated for each visit or study assessment (baseline, each post-baseline time point, endpoint) by treatment group.

The incidence of PCSA at any time will be summarized by treatment group for each vital signs variable. Shift tables showing changes with respect to the baseline status will be provided. Listings will be provided with flags indicating the out of range values as well as the PCSA values.

Assessment of potential drug-induced liver injury

The liver function tests, namely ALT, AST, alkaline phosphatase and total bilirubin, are used to assess possible drug induced liver toxicity. The proportion of patients with PCSA values at any post-baseline visit by baseline status will be displayed by treatment group for each parameter. The proportion of patients with PCSA values at any post-baseline visit will also be displayed by duration of exposure for each treatment group.

A graph of distribution of peak values of ALT versus peak values of total bilirubin will also be presented. Note that the ALT and Total bilirubin values are presented on a logarithmic scale. The graph will be divided into 4 quadrants with a vertical line corresponding to 3xULN for ALT and a horizontal line corresponding to 2xULN for total bilirubin.

Summarize the normalization by parameter (to ≤ 1 ULN or return to baseline) of elevated liver function tests by categories of elevation (1-<3x, 3x, 5x, 10x, 20x ULN for ALT and AST, 1.5x ULN for Alkaline phosphatase, and 1.5x and 2x ULN for total bilirubin), with following categories of normalization: never normalized, normalized after IMP discontinuation. Note that a patient will be counted only under the maximum elevation category. 1-3, 3-5, 5-10, 10-20, >20

Summarize the incidence of liver related AEs by treatment group. The selection of PTs will be based on standardized MedDRA query (SMQ) for drug related hepatic disorders.

Analysis of the electrocardiogram data

The summary statistics (including number, mean, median, standard deviation, minimum and maximum) of all ECG variables will be calculated for each visit or study assessment (baseline, each post baseline time point, endpoint) by treatment group.

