### ***General common rules***

All safety analyses will be performed on the safety population as defined in [Section 2.3.2](#), unless otherwise specified, using the following common rules:

- Safety data in patients who do not belong to the safety population (eg, exposed but not randomized) will be listed separately. The baseline value is defined in [Section 2.1.4](#).
- The potentially clinically significant abnormality (PCSA) values are defined as abnormal values considered medically important by the Sponsor according to predefined criteria/thresholds based on literature review and defined by the Sponsor for clinical laboratory tests, vital signs, and ECG (PCSA version dated March 2014 [[Appendix A](#)]).
- PCSA criteria will determine which patients had at least 1 PCSA during the TEAE period, taking into account all evaluations performed during the TEAE period, including unscheduled or repeated evaluations. The number of all such patients will be the numerator for the on-treatment PCSA percentage.
- The treatment-emergent PCSA denominator by arm for a given parameter will be based on the number of patients assessed for that given parameter in the TEAE period by treatment arm on the safety population.
- For quantitative safety parameters based on central laboratory/reading measurements, descriptive statistics will be used to summarize results and change from baseline values by time point and treatment arm. Summaries will include the endpoint baseline value, the last on-treatment value and change from baseline, the worst on-treatment value and change from baseline. The last on-treatment value is commonly defined as the last value collected during the treatment period (see [Section 2.1.4](#)). The worst on-treatment value is defined as the nadir and /or the peak post-baseline during the treatment period according to the direction (minimum or maximum) of the abnormality as defined in the PCSA list.
- All measurements (scheduled or unscheduled) will be re-allocated as given in [Section 2.5.4](#) and re-allocated visits measurements will be included in the by-time point summary.
- The analysis of the safety variables will be essentially descriptive and no systematic testing is planned. Relative risks versus placebo and their 95% CIs may be provided, if relevant.

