## **2.5.4 Windows for time points**

Data analyzed by time point (including efficacy, PK, BM, ADA, safety) will be summarized using the analysis windows given in [Table 6](#), [Table 7](#) and [Table 8](#). The analysis windows will be exhaustive so that data recorded at any time point (including unscheduled visits) has the potential to be summarized. These analysis windows will be applicable for all analyses (except for disease progression, all-cause mortality, IPF-related cause mortality, acute IPF exacerbations, respiratory hospitalizations, non-elective hospitalizations), and they are defined to provide more homogeneous data for time point-specific analyses. For efficacy, PK, BM, ADA, if multiple valid values of a variable exist within an analysis window, the nearest from the targeted study day will be selected. In case of ties, the maximum value will be displayed. For safety, if multiple valid values of a variable exist within an analysis window, the nearest from the targeted study day will be selected. In case of ties, the mean will be displayed.

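### The lung-function windows in SAP Table 6 are also applied to safety data, so early vital signs, laboratory and ECG visits have no row of their own and can be shown as Week 12; the injection-site time variable is also unusable as written

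*SAP*

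**What the plan says.** SAP 2.5.4, Table 6, defines five post-baseline windows: Week 12 (target Day 85, Days 2 to 126), Week 24 (169, 127 to 210), Week 36 (253, 211 to 308), Week 52 (365, 309 to 406) and Week 64 (449, after Day 406). Its footnote says "Note: Safety and BM will follow the same analysis windows". The general rules in SAP 2.4.5 send all safety measurements through Section 2.5.4, so that "re-allocated visits measurements will be included in the by-time point summary". Section 2.5.4 then says: "For safety, if multiple valid values of a variable exist within an analysis window, the nearest from the targeted study day will be selected". Tables 7 and 8 cover pharmacokinetics and anti-drug antibodies only, so there is no other window for safety.

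The schedule is denser than Table 6. Footnote f of the Protocol 1.2 flow chart says that blood pressure, heart rate and weight "will be measured at screening, baseline and every subsequent visit", which includes Weeks 2, 4 and 6. The flow chart and Protocol 10.1.4 place routine laboratory tests and ECG at Week 4, but not at Weeks 2 or 6.

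Protocol 11.4.3 plans that for quantitative safety parameters "descriptive statistics will be used to summarize results and change from baseline values by visit and treatment group", and that summary statistics "of all laboratory variables will be calculated for each visit or study assessment" and likewise "of all vital signs variables will be calculated for each visit or study assessment".

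On a separate matter, SAP 2.4.5.1 (treatment-emergent AESIs) plans a Kaplan-Meier curve for the first local injection-site reaction. It derives the time as the randomization date less the date of the last injection.

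**The concern.** Table 6 fits lung function, which is first measured after baseline at Week 12. Safety follow-up starts at Week 2. Putting everything from Day 2 to Day 126 under one Week 12 label, with one value kept, leaves two outcomes for the early measurements. They disappear from the by-time-point tables when a Week 12 value exists, or they stand in for Week 12 when nothing nearer Day 85 does.

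The vital-sign tables would therefore begin at Week 12 instead of Week 2, and the laboratory and ECG tables at Week 12 instead of Week 4. The Week 12 row would mix values from about Day 85 with earlier values, mostly from patients who left early. SAP 1.5, which lists the major departures from the protocol's statistical section, does not mention dropping these time points, so this looks like an oversight.

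The injection-site formula is a different kind of error. The reaction date does not enter it, so no curve of time to reaction can be built from it.

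**Working it through.** **Inputs.** Target days and windows: SAP Table 6. Day 1 is the first injection (SAP 2.5.1), so Week w is Day 7w + 1. Visit tolerance: plus or minus 2 days (Protocol 1.2, footnote a). Schedule: Protocol 1.2 flow chart.

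**Reproducing Table 6.** The boundaries are midpoints between consecutive target days, with the midpoint day given to the later window:

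- Week 24 starts at (85 + 169)/2 = 127
- Week 36 starts at (169 + 253)/2 = 211
- Week 52 starts at (253 + 365)/2 = 309
- Week 64 starts at (365 + 449)/2 = 407

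With a start at Day 2, this gives all five windows exactly.

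**Placing the early safety visits.**

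| Visit | Scheduled day | Range with ±2 days | Table 6 window | Distance from Day 85, on schedule (range) |
|---|---|---|---|---|
| Week 2 | 15 | 13–17 | Week 12 | 70 (68–72) |
| Week 4 | 29 | 27–31 | Week 12 | 56 (54–58) |
| Week 6 | 43 | 41–45 | Week 12 | 42 (40–44) |
| Week 12 | 85 | 83–87 | Week 12 | 0 (0–2) |

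The closest an in-window early visit can come to the target is 85 − 45 = 40 days. An on-schedule Week 12 visit is at most 2 days away, so it always wins. Scheduled visits from Week 12 onward fall in their own windows.

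**Rows lost.** Vital signs have eight scheduled post-baseline time points (Weeks 2, 4, 6, 12, 24, 36, 52, 64), and three have no row. Laboratory tests and ECG have six (Weeks 4, 12, 24, 36, 52, 64), and one has no row.

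**The same midpoint rule applied to the safety schedule.**

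- Vital signs: Week 4 starts at (15 + 29)/2 = 22, Week 6 at (29 + 43)/2 = 36, Week 12 at (43 + 85)/2 = 64
- Laboratory tests and ECG: Week 12 starts at (29 + 85)/2 = 57

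**Injection-site formula.** Take a patient randomized and first dosed on Day 1 and last dosed on Day 365. The derived time is 1 − 365 = −364 days, whether or not a reaction occurred and whatever its date. Since injections follow randomization, the result is zero (a single injection on the day of randomization) or negative for every treated patient.

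**The case against.** The strongest reply is that little depends on these tables. Safety analysis is descriptive, with no systematic testing. Counts of potentially clinically significant abnormalities use every evaluation in the treatment-emergent period. Worst on-treatment values are planned for central laboratory parameters (SAP 2.4.5) and for heart rate and blood pressure (2.4.5.4). Liver abnormalities are also shown by duration of exposure, and listings remain. This is right, and it confines the point to the by-time-point summaries. Coverage is not complete, however: weight is not among the vital signs given a worst value, and SAP 2.4.5.5 names none for ECG. That section does call ECG values central laboratory values, which could bring them under the general rule, but SAP 2.1.4.5 says ECGs are evaluated locally. On that reading, Week 4 ECG values survive only in the abnormality outputs and listings.

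A second reply is that mislabelling needs the absence of any value nearer Day 85. Patients who stop treatment should have the end-of-treatment assessments and be asked back for scheduled visits, and those who withdraw should, if possible, have the end-of-study assessments (Protocol 10.1, 10.3.4 and 10.3.5). This stands: mislabelling affects a subset whose size the documents do not allow one to estimate, and the 70-day case also requires Weeks 4 and 6 to be missing. The loss of rows, by contrast, applies to everyone with a Week 12 value.

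Third, the SAP speaks of time points where the protocol speaks of visits, and its windows do cover every day. The SAP may choose its rows, but it does not declare this choice. It also uses early time points elsewhere: Table 7 has a Week 4 row, and the exposure categories in 2.4.3.1 break at 2, 4, 6 and 12 weeks.

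Finally, the injection-site formula is plausibly a drafting slip and is unrelated to Table 6. Both are true; it still needs correcting before it is programmed.

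**Conclusion.** The point holds. As written, the SAP gives no row to 3 of 8 scheduled vital-sign time points and 1 of 6 laboratory/ECG time points. Where no nearer value exists, it labels an early value as Week 12, wrong by 42 days (Week 6), 56 days (Week 4) or 70 days (Week 2) for an on-schedule visit. This conflicts with the protocol's by-visit summaries. The day counts assume visits as scheduled, and the displacement result holds anywhere within the 2-day tolerance. The primary analysis, type I error and abnormality counts are unaffected. The injection-site time variable is wrong for every treated patient. Both should be corrected, but neither changes a confirmatory conclusion.

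**What to change.** Restrict the Table 6 note to biomarkers and SpO2 (SpO2 is first measured after baseline at Week 12), and add safety windows under the same midpoint rule:

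- Blood pressure, heart rate and weight: Week 2, Days 2–21; Week 4, Days 22–35; Week 6, Days 36–63; Week 12, Days 64–126.
- Laboratory tests and ECG: Week 4, Days 2–56; Week 12, Days 57–126.
- Later windows unchanged.

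Define time to first injection-site reaction as the date of the first treatment-emergent reaction minus the date of the first injection, plus 1. This uses the interval that SAP 2.4.5.1 already tabulates, and the added day follows the convention in SAP 2.1.3.2.2. Randomization and first injection are both scheduled at Visit 2, so the choice of origin should matter little. Keep the stated censoring dates for patients without a reaction, measured from the same origin, and say how a first reaction reported after a discontinued patient's last injection is handled.

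The cost is one small SAP table, one formula and a few extra rows in the safety tables. No new data are required.
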